- b) no new clinical symptoms and physical findings of IFD are noted at the current visit.

AND

- c) patient meets mycological criteria for Eradication or Presumed Eradication

- **Resolution-Partial:**

For patients with attributable clinical symptoms and physical findings of IFD present at baseline, Resolution-Partial is assigned if

- a) there is some persistence of the attributable clinical symptoms and physical findings of IFD noted either at baseline or at a subsequent prior post-baseline visit but there is improvement in at least some of these same symptoms and findings

AND

- b) no worsening of any of these same symptoms and findings

AND

- c) no new clinical symptoms and physical findings of IFD at the current visit.

For patients lacking attributable clinical symptoms and physical findings of IFD present at baseline*, Resolution-Partial is assigned if

- a) there is some persistence of the attributable clinical symptoms and physical findings of IFD noted at a subsequent prior post-baseline visit but there is improvement in at least some of these same symptoms and findings

AND

- b) no worsening of any of these same symptoms and findings
AND
- c) no new clinical symptoms and physical findings of IFD at the current visit.
AND
- d) patient meets mycological criteria for Eradication or Presumed Eradication.

** If the qualifying infection was diagnosed before baseline, data regarding the prior symptoms and prior evaluation(s) of the invasive fungal infection may need to be considered.*

- **Failure-Stable:** Neither worsening nor improvement in any attributable clinical symptoms and physical findings present at baseline or that appeared at a subsequent prior visit AND no new clinical symptoms and physical findings of IFD at the current visit.
- **Failure-Progression:** Shows EITHER worsening in one or more attributable clinical symptoms and physical findings present either at baseline or that appeared at a subsequent prior visit OR appearance of new clinical symptoms and physical findings of IFD at the current visit.
- **Results not available/patient unevaluable** (i.e. visit and/or assessment of clinical symptoms and physical findings of IFD was not performed).

Note that the rules defining success are tested in sequence beginning with Success-Complete.

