The Investigator will be asked to provide an assessment of the mycological response for each patient at Day 7, Day 42, Day 84/EOT and 4 weeks after EOT in the main study phase and at other visits as clinically indicated (*note that for patients planning to receive ET beyond Day 90, the Day 84 visit and the main study phase EOT visit will be combined into a single Day 84/EOS/EOT visit on approximately Day 90.*). Outside of these timepoints, mycological assessment will be performed as clinically indicated and/or in line with standard clinical management for the patient's specific IFD and anatomic site involved.

The Investigator will provide an assessment of the mycological response as follows:

- **Eradication** (eradication of the original causative organism cultured or identified by histology/cytology at baseline and no emergence of new causative organisms at that visit).
- **Presumed eradication** (missing documentation of the eradication of the original causative organism cultured or identified by histology/cytology at baseline and no documentation of emergence of new causative organisms at that visit plus resolution of all or some attributable clinical symptoms and physical findings of IFD present at baseline and/or of those that appeared at a subsequent visit and no appearance of new attributable clinical symptoms and physical findings of IFD at that visit).
- **Persistence** (persistence of the original causative organism cultured or identified by histology/cytology at baseline or emergence of a new causative organism at that visit).
- **Presumed persistence** (missing documentation of the persistence of the original causative organism cultured or identified by histology/cytology at baseline and no documentation of emergence of new causative organisms at that visit plus either (i) no resolution or (ii) worsening of any attributable clinical symptoms and physical findings of IFD present at baseline and/or of those that appeared at a subsequent visit and/or appearance of new attributable clinical signs and physical findings of IFD at that visit).
- **No mycological Follow-up results available**, for whatever reason (no diagnostic test done at the scheduled timepoint AND other data are insufficient to support assigning Presumed Eradication or Presumed Persistence).
- **No mycological evidence at baseline** (negative diagnostic test(s) results at baseline, or not done at baseline).

Mycological Response after Initial Success

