If relevant mycology findings occur after successful mycological response (proven or presumed eradication), an evaluation will be made as to whether the infection is recurrent (same species as at baseline) or emergent (different species compared with baseline). Patients with recurrent or

emergent infection will be classified as mycological failure from the visit onwards where positive cultures were reported.

Recurrent – Re-appearance of same species after apparent negative culture PLUS additional antifungal treatment becomes necessary.

Emergent – Appearance of new species after apparent negative culture PLUS additional antifungal treatment becomes necessary. New species emerging during the first 7 days of therapy with F901318 are presumed to have been present at baseline and are classified as Baseline secondary infections rather than Emergent infections.

6.3.1.5 *Investigator’s Assessment of Overall Response*

The Investigator’s assessment of overall response will be based on all available assessments (clinical, radiological and mycological) as described in Sections 6.3.1.1, 6.3.1.2 and 6.3.1.4. It is essential that the same methods and assessments are used to define the IFD diagnosis at baseline and to evaluate the response to treatment.

Treatment “success” is defined as **complete** or **partial**.

Treatment “failure” is defined as **stable** response or **progression** of IFD.

Of the three components of overall response, only clinical and mycological responses are required. Patients who lack data at a visit (e.g., the visit data were not collected for some reason) or who are not evaluable at the visit because these data cannot be collected are considered failures.

The criteria for assessment of overall response are summarised in Table 5:

Table 5 Criteria for Assessment of Overall Response

Success - complete*:
	
 • Clinical: Meets criteria for Resolution-Complete; AND • Radiological (if assessed): Shows resolution of radiological abnormalities ($\geq 90\%$ response); AND • Mycological: Meets criteria for presumed or documented eradication.

Success - partial*:
	
 • Clinical: Meets criteria for Resolution-Complete or Resolution-Partial; AND • Radiological (if assessed): Shows resolution or improvement of radiological abnormalities (at least 25% response); AND • Mycological: Meets criteria for presumed or documented eradication.

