
Failure - stable:
	
 • Clinical: No improvement and no worsening of any attributable clinical symptoms and physical findings previously noted and no new attributable clinical symptoms or physical findings of IFD (Failure-Stable); OR • Radiological: Shows no evidence of progression OR $< 25\%$ improvement of radiological abnormalities; OR • Mycological: Had mycological evidence at baseline AND does not meet criteria for presumed or documented eradication.

Failure - progression:
	
 • Clinical: Either worsening of attributable clinical symptoms or physical findings of IFD or appearance of new attributable symptoms or findings of IFD (Failure-Progression); OR • Radiological: Worsening or new radiological abnormalities; OR • Mycological: Has mycological evidence for a recurrent or emergent IFD, OR alternative systemic antifungal treatment required.

*For these categories, the only required data are the clinical and mycological data. The absence of radiological evaluations at a given time point does not prevent assignment to Success-Complete or Success-Partial. The rules defining success are tested in sequence with Success-Complete assigned if its rules are met and Success-Partial otherwise assigned.

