Based on the DRC-adjudicated and Investigator-assessed mycological response categorized as Success/Failure, a response rate will be calculated based on all patients included in the mITT population with a baseline culture result available. Patients with a mycology evaluation of “No mycological Follow-up results available” will be assigned an outcome of presumed eradication if they are deemed a clinical success and a presumed failure if they are deemed a clinical failure, or clinical response is missing. Mycological success will include patients classified as a success or a presumed eradication. In addition a 95% CI for a single binomial proportion will be calculated.

All-cause mortality at Day 42, main study phase EOT, Day 84 and 4-week FU*

Mortality rates will be derived at Day 42, main study phase EOT, Day 84 and 4-week FU* based on all patients in the mITT population. In addition a 95% CI for a single binomial proportion will be calculated. Also, Kaplan-Meier analyses will be performed at Day 42, main study phase EOT, Day 84 and 4-week FU*, summarising median time to death (stratified by DRC-adjudicated disease category). A reported death will be carried forward for all future visits. A patient without reported death for the specific visit analysed (Day 42, main study phase EOT, Day 84 or 4-week FU*) will be censored for the specific visit analysed.

**Note: For patients planning to receive ET beyond Day 90, the Day 84 visit and the main study phase EOT visit will be combined into a single Day 84/EOS/EOT visit on approximately Day 90 and there will be no 4-week FU visit in the main study phase. As judged relevant, subanalyses will be performed to account for this difference in observation periods.*

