Presumed Eradication	Missing documentation of the eradication of the original causative organism cultured or identified by histology/cytology at baseline and no documentation of emergence of new causative organisms at that visit plus resolution of all or some attributable clinical symptoms and physical findings of IFD present at baseline and/or of those that appeared at a subsequent visit and no appearance of new attributable clinical symptoms and physical findings of IFD at that visit.

Document: \\weedc-vnasc01\BIOSdata\F2G\F901318\ [Redacted]
Author: [Redacted] Version Number: 3.0
Version Date: 06Apr2023
Template No.: CS_TP_BS016 Revision 6 Reference: CS_WI_BS005
Effective Date: 02Dec2019

F2G Ltd.
PROTOCOL F901318/0032

Persistence	Persistence of the original causative organism cultured or identified by histology /cytology at baseline or emergence of a new causative organism at that visit
Presumed Persistence	Missing documentation of the persistence of the original causative organism cultured or identified by histology/cytology at baseline and no documentation of emergence of new causative organisms at that visit plus either (i) no resolution or (ii) worsening of any attributable clinical symptoms and physical findings of IFD present at baseline and/or of those that appeared at a subsequent visit and/or appearance of new attributable clinical signs and physical findings of IFD at that visit.
No Mycological Follow-up Results Available	For whatever reason no diagnostic test done at the scheduled timepoint AND other data are insufficient to support assigning Presumed Eradication or Presumed Persistence).
No Mycological Evidence at Baseline	Negative diagnostic test(s) results at baseline, or not done at baseline.
Recurrent	Re-appearance of same species after apparent negative culture PLUS additional antifungal treatment becomes necessary.
Emergent	Appearance of new species after apparent negative culture PLUS additional antifungal treatment becomes necessary. New species emerging during the first 7 days of therapy with F901318 are presumed to have been present at baseline and are classified as Baseline secondary infections rather than Emergent infections.

Patients with a mycological evaluation of “No Mycological Follow-up Results Available” and “Not Done” at a specific visit will be assigned an outcome of:

- “Presumed Eradication” if they are a clinical success at the specific visit,

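### With no repeat specimen, presumed eradication needs a symptom to resolve but clinical Resolution-Partial needs only improvement, so a patient improved with nothing resolved gets conflicting Day 42 classifications

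*Protocol*

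**What the plan says.** **Clinical response.** Protocol 6.3.1.1 and SAP Table B assign Resolution-Partial to a patient with baseline symptoms when some persist but "there is improvement in at least some of these same symptoms and findings", none is worse and none is new. No symptom has to disappear. SAP 16.1.5.3 counts Resolution-Partial as a clinical success.

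**Mycological response without a specimen.** Protocol 6.3.1.4 and SAP Table D give two presumed categories.
- Presumed eradication: no documentation of eradication or of a new organism, "plus resolution of all or some attributable clinical symptoms and physical findings of IFD present at baseline", and no new symptoms.
- Presumed persistence: no documentation, "plus either (i) no resolution or (ii) worsening of any attributable clinical symptoms and physical findings of IFD present at baseline", or new signs.

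A further category, no follow-up results available, is kept for cases with no test where the other data cannot support either presumed category.

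**Overall response.** Both success rows of Protocol Table 5 (section 6.3.1.5) and SAP Table A carry the condition "Mycological: Meets criteria for presumed or documented eradication". The mycological route to Failure-Stable is "Had mycological evidence at baseline AND does not meet criteria for presumed or documented eradication".

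**Assignment rule.** Under Protocol 8.8.2, patients with no mycological follow-up results "will be assigned an outcome of presumed eradication if they are deemed a clinical success". SAP 16.1.5.5 extends this to entries of *Not Done*, giving presumed eradication "if they are a clinical success at the specific visit" and presumed persistence to clinical failures.

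**The concern.** The same symptoms are judged by two standards within one composite. Improvement is enough for the clinical component. The mycological component, when inferred from those symptoms, asks for resolution. A patient can therefore pass the first and fail the second with no mycological information involved.

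The SAP also offers two routes with opposite answers. Section 16.1.6.1 refers a missing mycological response to the Table D criteria, which read literally give presumed persistence. The assignment rule in 16.1.5.5 gives presumed eradication.

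The primary endpoint is the DRC-adjudicated overall response at Day 42. It is to be compared with historical rates (SAP 16.1.3), and the initial analysis is meant to inform whether approval might be sought on these data (Protocol 8.1). Its success definition should have one reading.

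The group is a plausible one. Protocol 6.3.1.4 records follow-up cultures from non-bloodstream infections only if they are obtained. Section 4.2 expects some patients to have benefited without complete resolution even after 84 to 90 days.

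**Working it through.** The plan states no figure on this point, so there is nothing to reproduce. The check applies the rules to each possible patient and then bounds the effect.

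**Step 1: classification.** Take a patient with attributable symptoms and mycological evidence at baseline, no repeat specimen, no new or worse symptoms, no new organism, and radiology not assessed.

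| Symptoms at Day 42 | Clinical | Mycology, literal 6.3.1.4 / Table D | Overall | Mycology, 8.8.2 / SAP 16.1.5.5 | Overall if that rule is applied |
|---|---|---|---|---|---|
| All resolved | Resolution-Complete | Presumed eradication | Success | Presumed eradication | Success |
| At least one resolved, rest persist | Resolution-Partial | Presumed eradication | Success | Presumed eradication | Success |
| Improved, none resolved | Resolution-Partial | Presumed persistence | Failure-Stable | Presumed eradication | Success |
| Unchanged | Failure-Stable | Presumed persistence | Failure | Presumed persistence | Failure |

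The rules disagree only in the third row.

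**Step 2: does the assignment rule reach that row?** Under 8.8.2 it applies to the no-results category, which requires that neither presumed category can be assigned. Read literally, the third-row patient already has presumed persistence and never reaches the rule. The SAP's *Not Done* is not a Table D category and has no such restriction, so it could capture the same patient. The answer then depends on how the missing test was recorded.

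**Step 3: one symptom resolved, another worse, none new.** Presumed eradication has no condition against worsening, so it is met. Presumed persistence names worsening, so it is met too. The clinical category is Failure-Progression, which rules out overall success. The overlap therefore affects only the secondary mycological response.

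**Step 4: size.** The documents give neither the share *g* of patients in the third row nor a base rate. Assume a 30% success rate with these patients counted as failures, and *g* of 2%, 5% or 10%. If all of them became successes, x = n(0.30 + g). The exact 95% limits are the 0.025 quantile of Beta(x, n − x + 1) and the 0.975 quantile of Beta(x + 1, n − x).

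| g | n = 100 | n = 200 |
|---|---|---|
| 0 | 30/100 = 30.0% (21.2–40.0) | 60/200 = 30.0% (23.7–36.9) |
| 2% | 32/100 = 32.0% (23.0–42.1) | 64/200 = 32.0% (25.6–38.9) |
| 5% | 35/100 = 35.0% (25.7–45.2) | 70/200 = 35.0% (28.4–42.0) |
| 10% | 40/100 = 40.0% (30.3–50.3) | 80/200 = 40.0% (33.2–47.1) |

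These are upper bounds. Where radiology is assessed, Table 5 also requires at least 25% improvement, and patients below that fail under either rule.

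**The case against.** **A coherent reading exists.** The protocol itself calls the improvement category Resolution-Partial, so resolution of all or some symptoms can be taken to mean Resolution-Complete or Resolution-Partial. The 8.8.2 and 16.1.5.5 rules point to the same intent. The amendment history suggests that the clinical categories were once worded in terms of resolution and were changed while the presumed categories were not. That history describes superseded text and is evidence of meaning only. This stands: the likely intent is visible. The current text does not state it, and an adjudicator applying Table D as written reaches the other answer.

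**The endpoint is adjudicated.** The Day 42 response is held in a separate DRC database, the assignment rules are written for the secondary mycological endpoint, and the DRC charter is not among the documents. A reader might infer that the ticked mycology field by itself changes the primary result. The documents do not say that the committee's overall response is recomputed from imputed components, so that inference goes too far. Even so, the SAP sets out Table A for the primary endpoint and Table D for DRC mycology, and the conflict lies in those tables.

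**The plan already bounds it.** SAP 16.1.1 includes an analysis counting Failure-Stable as success, which takes in these patients. That helps only in part, because it also takes in unchanged patients. The modified response in SAP 16.1.4 relaxes radiology alone and keeps the eradication requirement. The literal rule also lowers a single-arm response rate, so it errs against the drug.

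**Conclusion.** The definitions conflict for one group: patients with attributable symptoms and mycological evidence at baseline, no repeat specimen, and improvement without any symptom resolving. Read literally they are overall Failure-Stable at Day 42; under the assignment rule, if it governs, they can be successes.

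A reader might infer that every improved patient without a repeat specimen fails. The text does not support that, because one resolved symptom is enough for presumed eradication. Nor does the missing bar on worsening let a progressing patient count as an overall success. It leaves the secondary mycological category undetermined for that patient. To say it inflates that rate would assume that assessors choose eradication over a persistence category that names worsening.

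The size is unknown. The shifts of at most 2, 5 and 10 percentage points rest on assumed shares of 2%, 5% and 10%, an assumed 30% base rate, and radiology never being the limiting component.

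**What to change.** In Protocol 6.3.1.4 and SAP Table D, for patients with attributable baseline symptoms and no follow-up culture or histology, replace the symptom clauses with the clinical category at that visit:
- Presumed eradication: Resolution-Complete or Resolution-Partial.
- Presumed persistence: Failure-Stable or Failure-Progression.

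Keep the condition that no new organism is documented. This is the rule already in Protocol 8.8.2 and SAP 16.1.5.5. It also removes the overlap in Step 3, because a patient with a worse symptom is Failure-Progression.

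Limit the change to patients with baseline symptoms. For those without, the clinical category itself depends on eradication, and the definition would become circular.

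State in SAP 16.1.1, and in a note to the DRC, that this rule governs the Day 42 overall response.

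The cost is a few lines of text and no new data. Any cases in this group already adjudicated would need a second look. The drawback is that the primary success definition becomes slightly more lenient than the literal text, so report how many patients change category and the Day 42 rate under both readings.

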6.3.2 Survival

All-cause mortality has been used historically as an endpoint in other similar clinical studies in IFD. All-cause mortality will be assessed using survival status and, if applicable, death details will be recorded in the eCRF. If the patient has died, the date and cause of death will be recorded, in addition to details required for SAE reporting (see Section 6.4.1.2).

Survival status will be recorded at Day 42, main study phase EOT, Day 84 and at the 4-week FU and included in the CSR. Information on survival status on Days 42 and 84 will be collected in all

patients, irrespective of when treatment was discontinued (*note that for patients planning to receive ET beyond Day 90, the Day 84 visit and the main study phase EOT visit will be combined into a single Day 84/EOS/EOT visit on approximately Day 90*).

Survival status will also be recorded at each ET visit and at the post-ET FU visit, and will be presented in the report addendum.

6.3.3 Data Review Committee Assessment of Overall Response

Independent assessment of overall response during the main study phase will be performed by the DRC for visits up to Day 84/Day 90, and for the post-treatment FU visit for patients who do not receive ET. The DRC will not assess overall response at any ET visits or at the post-ET FU. Details of the process and overall response definitions will be documented in the DRC charter.

6.3.4 Patient-Reported Outcomes

Patient-reported outcomes will be assessed in this study using the EQ-5D-5L questionnaire. The EQ-5D-5L questionnaire will be completed by the patient during screening to provide a baseline, at the Day 42 and Day 84/EOT main study phase visits, and every 4 weeks during the ET phase.

The questionnaire, translated as required in the local language, will be distributed by the site staff but completed entirely by the patient. To ensure instrument validity and that data standards meet health authority requirements, the questionnaire should be self-administered and checked for completion at the site staff prior to the completion of other study assessments.

